9.3 Definition of Populations

HIV infected men and women with either previously documented HSIL or abnormal anal cytology within the past 2 years.

Please see section 4.1 and 4.2 for inclusion and exclusion criteria description

9.4 Interim Analyses and Stopping Rules

N/A

9.5 Outcomes

9.5.1 Primary Outcome

The primary outcome are the performance characteristics: SN, SP, PPV, NPV

9.5.2 Secondary Outcomes

The first secondary outcome is efficiency (number of potential biopsies averted, reduction in procedure time).

The second secondary outcome is to develop and optimize i) a mobile highresolution microendoscope (mHRME) and 3D image mapping for anal HSIL diagnosis and ii) image-analysis software during HRA.

9.6 Data Analyses

Objective 1. We will determine the performance characteristics of mHRME for the prediction of anal HSIL in flat mucosa and mucosal lesions using histopathology as the gold standard. Our hypothesis is that the sensitivity (SN) specificity (SP), positive predictive value (PPV) and negative predictive value (NPV), as well as the receiver operating curve for the identification of neoplasia on a per biopsy and per patient basis will be high. We will first compare the HRA-directed biopsy (as the gold standard) to the results of the mHRME HSIL diagnosis. The SN of mHRME diagnosis in detection of HSIL will be estimated with the binomial proportion of study participants who are positive for HSIL on HRA-guided biopsy at two thresholds of histology thresholds which are: 1) AIN 2+ threshold, and 2) AIN3+ threshold. SP will be estimated as the proportion of study participants who are negative for HSIL on HRA-guided biopsy at both thresholds. Positive and negative predictive values will be estimated using the binomial proportion and its 95% CI. In addition, the Cohens kappa statistic, and receiver operator characteristic curves will be generated if patient characteristics such as low CD4 count, cART utilization, or high HIV viral load impact the determination of SN and SP. The lab information will be collected and placed in the source document and entered in Oncore. SN and SP of mHRME-based HSIL diagnosis will be estimated on a per lesion and per patient basis with 95% confidence intervals and compared by McNemar's test. A generalized linear model for logistic regression with multiple correlated outcomes will compare SN and SP of each method on a per biopsy and per patient basis. For Device optimization: No Data Analyses are planned.

Objective 2a. Determine clinical efficiency of mHRME + HRA for the diagnosis of HSIL. Clinical efficiency is defined as: `Diagnostic Yield: Percent of HRME diagnosed HSIL lesions that were classified as non-HSIL by clinician. `Biopsies averted: Percent of HRAvisualized lesions that the clinician originally categorized as potentially needing a biopsy but on mHRME were appropriately down-graded, averting an unnecessary biopsy. Procedure time: Total procedure time (mHRME and HRA). For Diagnostic Yield and Biopsies Averted, we will estimate 95% confidence intervals. Total procedure time will be recorded. mHRME Procedure time will measured separately once mHRME is initiated. Median and standard deviation of procedure times and mHRME procedure times will be calculated.

Objective 2b. Images collected from the 50 patients will be compared to biopsies. Preliminary Sensitivity, Specificity, positive predictive value (PPV) and negative predictive values (NPV) will be estimated and precision of interval width calculations will be done.

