9. STATISTICAL CONSIDERATIONS

9.1 General Design Issues

The primary outcome of this cross- sectional study is to measure the operating characteristics including SN, SP, PPV and NPV comparing the physician- and algorithm-guided HRME-based image compared to the Lugol's- guided physician diagnosis of HSIL during HRA.

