9.2 Sample Size and Randomization

The study will primarily be powered to determine the precision around the operating characteristics of mHRME imaging. We estimate that because the median number of lesions per patient is approximately 1.5-2, and HSIL prevalence of 30%, approximately 150 patients (225-300) lesions will be needed to estimate the confidence intervals around SN and SP estimates see Table 1 below. In order for 150 patients to complete study procedures, we will target a total enrollment of 200, because we will also be improving the technology as a secondary objective and assume that up to 30% of patients may not have evaluable optimized HRME images.

Precision calculation

The damage to precision due to within-subject correlation is mitigated by the fact that the average number of per-patient slides is at most 2. Correlation = 0.5 is a high estimate, but the table below shows precision values close to the original independence-assumption based ones.

SN/SP estimate	¹ / ₂ width CI for 225 slides		¹ / ₂ width CI for 300 slides		
	indep	$\operatorname{corr} = 0.5$	indep	corr = 0.5	
10%	4.66%	6.99%	3.94%	5.91%	
15%	5.28%	7.93%	4.50%	6.75%	
20%	5.74%	8.61%	4.91%	7.37%	
25%	6.07%	9.10%	5.21%	7.82%	
30%	6.30%	9.46%	5.43%	8.14%	
35%	6.46%	9.69%	5.57%	8.35%	
40%	6.54%	9.81%	5.65%	8.47%	
45%	6.55%	9.82%	5.67%	8.50%	
50%	6.50%	9.74%	5.63%	8.45%	
55%	6.55%	9.82%	5.67%	8.50%	
60%	6.54%	9.81%	5.65%	8.47%	
65%	6.46%	9.69%	5.57%	8.35%	
70%	6.30%	9.46%	5.43%	8.14%	
75%	6.07%	9.10%	5.21%	7.82%	
80%	5.74%	8.61%	4.91%	7.37%	
85%	5.28%	7.93%	4.50%	6.75%	

Treatment Assignment Procedures

All participants will undergo HRME-imaging prior to biopsy

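### Section 9.6 names McNemar's test per lesion and a plain binomial interval for PPV and NPV without allowing for several lesions per patient; the correlated-outcomes model planned alongside covers only the SN/SP comparison

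*Combined protocol and SAP*

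**What the plan says.** Section 9.5.1 makes SN, SP, PPV and NPV the primary outcome, and 9.2 sizes the study for the precision of SN and SP. The Objective 1 paragraph of 9.6 contains four relevant statements.

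- The hypothesis covers all four measures "for the identification of neoplasia on a per biopsy and per patient basis will be high".
- SN and SP are "estimated on a per lesion and per patient basis with 95% confidence intervals and compared by McNemar's test". No comparator and no interval formula is named.
- "Positive and negative predictive values will be estimated using the binomial proportion and its 95% CI". The unit is not stated.
- The sentence after the McNemar sentence adds: "A generalized linear model for logistic regression with multiple correlated outcomes will compare SN and SP of each method on a per biopsy" and per-patient basis. The correlation structure is not described.

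On the comparator, 9.1 sets the physician- and algorithm-guided HRME reads against the Lugol's-"guided physician diagnosis of HSIL during HRA".

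On clustering, 9.2 tabulates half-widths under independence and at a correlation of 0.5. It says that "Correlation = 0.5 is a high estimate" and that the loss of precision is limited because "the average number of per-patient slides is at most 2".

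**The concern.** Lesions from one patient share a host, an operator and an imaging session, so correct and incorrect reads tend to cluster. An ordinary McNemar test and a plain binomial interval treat every lesion as independent. The planning section takes this seriously, but the analysis section does not carry it through to every primary measure.

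This study is sized for precision, so the intervals are the main result. An analyst following 9.6 at lesion level could report intervals that are too narrow. The same analyst would also hold two per-biopsy SN/SP comparisons, one ignoring clustering and one presumably not, with no rule for which is reported.

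**Working it through.** **The plan's own figures.** The independent columns of the 9.2 table match a 95% interval on the logit scale, taking the longer arm. At 85% and 225 slides: logit(0.85) = 1.7346; 1.96/sqrt(225 × 0.85 × 0.15) = 0.3659; the back-transformed lower limit is 79.72%, so the half-width is 5.28 points, as printed. The same steps at 300 slides give 4.50, as printed. The correlated columns are these values times 1.5: 7.93 and 6.75, as printed. The factor 1.5 = 1 + (2 − 1) × 0.5 is a variance inflation. The half-width should grow by its square root, 1.225, which gives 5.28 × 1.225 = 6.47 and 4.50 × 1.225 = 5.51. So 7.93 against 5.28 is not the cost of clustering.

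**Inputs.** From 9.2: 150 patients, 1.5 to 2 sites each (225 to 300), 30% HSIL, correlation 0.5. Assumed: the 30% applies per site; HSIL status does not cluster within patients; accuracy is 85% (the last row of the 9.2 table); an average of 1.5 means half the patients have one site and half have two.

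**Design effect within each class.** Only sites of the same histological class enter SN or SP, so DE = 1 + ρ × (E[n²]/E[n] − 1), where n is the patient's number of sites in that class.

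- Two sites: E[n²]/E[n] − 1 is 0.3 for HSIL and 0.7 for non-HSIL. DE = 1.15 (SN) and 1.35 (SP).
- 1.5 sites: the terms are 0.3/1.5 = 0.20 and 0.7/1.5 = 0.467. DE = 1.10 (SN) and 1.23 (SP).

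**Half-widths and coverage.** Half-width = 1.96 × sqrt(0.85 × 0.15/n) × sqrt(DE). Coverage of the unadjusted interval is about 2Φ(1.96/sqrt(DE)) − 1.

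| Measure, total sites | n | Unadjusted | Clustered | Coverage |
|---|---|---|---|---|
| SN, 225 | 67.5 | 8.52 | 8.93 | 93.8% |
| SN, 300 | 90 | 7.38 | 7.91 | 93.2% |
| SP, 225 | 157.5 | 5.58 | 6.19 | 92.2% |
| SP, 300 | 210 | 4.83 | 5.61 | 90.8% |

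Simulation with Wilson intervals agrees: SP 90.1-92.6%, SN 93.1-94.4%, PPV 91.6-93.7%, NPV 93.2-94.4%. At ρ = 0.3 the formula gives DE 1.14 and 1.21 for SP (coverage 93.4% and 92.5%) and 1.06 and 1.09 for SN (94.3% and 94.0%). If HSIL status also clusters at 0.5, simulated coverage at ρ = 0.5 is about 90-92% (SP), 91-93% (SN), 89-92% (PPV) and 90-93% (NPV).

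**McNemar per lesion.** This was simulated at ρ = 0.5 with equal true accuracy of the two reads and unclustered HSIL. Type I error is 7.7-9.4% (SP) and 6.5-7.3% (SN) when the two reads' patient effects are independent. It is 5.6-6.6% and 4.6-5.3% when those effects correlate at 0.9. A different set-up, pooling both classes and correlating the paired differences themselves at 0.5, gives about 12% with two lesions each.

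**Against the 9.2 figures.** Clustered SP (6.19 and 5.61) lies inside 7.93 and 6.75. On the plan's own logit, longer-arm construction it is 7.29 and 6.51, still inside. SN (8.93 and 7.91) lies outside, and so do its unadjusted values (8.52 and 7.38), because 9.2 uses all slides as the SN denominator. That is a separate issue.

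**The case against.** A reader might infer that 9.6 makes no allowance for clustering at all. The text does not support that: the sentence after the McNemar sentence plans a model for correlated outcomes, per biopsy. What stands is that the model is limited to comparing SN and SP, is not ranked against McNemar's test, and leaves PPV and NPV out. Its wording could also mean two methods on one lesion rather than lesions within a patient.

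A reader might also infer that the SN and SP intervals are specified as unadjusted. They are not; no per-lesion formula is given. The SN sentence that uses a binomial proportion speaks of the "binomial proportion of study participants who are positive for HSIL on HRA-guided biopsy at two thresholds", where such an interval is acceptable. Likewise the PPV/NPV sentence may be meant per patient. These objections hold, so the coverage figures are conditional on unadjusted methods being used per lesion. They do not close the gap, because the hypothesis in the same paragraph covers all four measures per biopsy.

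The effect is also small and depends on assumptions. The plan itself calls 0.5 high, no decision threshold hangs on the results, and the correlation between the two reads' patient effects is not given. Cluster size is unsettled too: 5.1 adds at least one Lugol's-positive biopsy per patient but still quotes 225 to 300 images. If that site came on top of the 1.5 to 2, was always non-HSIL and shared ρ = 0.5, the SP design effect would be 1 + 0.5 × (4.64/2.05 − 1) = 1.63 or 1 + 0.5 × (6.18/2.4 − 1) = 1.79, with coverage near 88% or 86%. The documents do not settle which count applies.

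**Conclusion.** The point holds in a limited form and should be fixed. At lesion level 9.6 names one comparison that ignores clustering beside another that may handle it, leaves the SN/SP interval method unstated, and gives PPV and NPV a binomial interval without a unit.

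If unadjusted methods are used per lesion, nominal 95% intervals cover about 90-93% (SP), 92-94% (PPV) and 93-94% (SN and NPV) at a correlation of 0.5, and the loss is small at 0.3. McNemar type I error lies between near nominal and about 9%. This rests on 150 patients, 1.5 to 2 sites each, 85% accuracy and 30% HSIL per site without clustering of HSIL status. The per-patient analyses are not affected. The printed 7.93% against 5.28% should not be quoted as the size of the problem.

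**What to change.** - Take all per-lesion SN, SP, PPV and NPV intervals from one patient-clustered method: GEE with robust standard errors, or a patient-level bootstrap.
- Make the planned correlated-outcomes model, clustered by patient, the only lesion-level comparison of SN and SP, and name its comparator.
- Keep McNemar's test and binomial intervals for the per-patient analysis, and state the unit wherever PPV and NPV are reported.

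The cost is a few sentences of SAP text and standard code, with no extra patients. Per-lesion intervals become wider by a factor of about 1.05-1.2 at a correlation of 0.5. In a simulation check at that correlation, patient-clustered robust intervals covered 94.4-95.9% for all four measures. The change does not remedy the SN precision shortfall against 9.2, which needs its own correction.

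### Diagnostic Yield has no histology condition, so mHRME false positives can count as efficiency gain, and the named reduction in procedure time is never estimated

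*Combined protocol and SAP*

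**What the plan says.** Section 9.5.2 gives the first secondary outcome as "efficiency (number of potential biopsies averted, reduction in procedure time"; section 1.2(a) says the same. Section 9.6, Objective 2a, turns clinical efficiency into three measures:

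- Diagnostic Yield: "Percent of HRME diagnosed HSIL lesions that were classified as non-HSIL by clinician".
- Biopsies Averted: the share of HRA-visualised lesions first marked as possibly needing biopsy and then *appropriately* down-graded on mHRME. The standard for that adverb is not named.
- Procedure time: "Total procedure time (mHRME and HRA", with the mHRME part handled thus: "mHRME Procedure time will measured separately once mHRME is initiated".

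Confidence intervals are planned for the first two. For time the plan is: "Median and standard deviation of procedure times and mHRME procedure times will be calculated".

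Histology will be available. Section 5.1 has a biopsy at each image site, and section 10.3.3 describes a consensus pathology read. Objective 1 in section 9.6 uses histopathology as its reference, at two cut-offs: "1) AIN 2+ threshold, and 2) AIN3+ threshold". In Appendix 1 (Manual of Operations, step 19) the clinician's HRA read and plan are recorded at each abnormal area before mHRME starts. A second clinician read and plan, based on the mHRME image, follows.

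**The concern.** Diagnostic Yield is meant to show what mHRME finds that the clinician missed. As defined, it shows where mHRME says HSIL and the clinician does not, whichever of them is right. Some of what is reported as gain may be mHRME error at sites the clinician read correctly. The measure is not listed in sections 1.2 or 9.5.2, but section 9.6 makes it part of clinical efficiency and gives it a 95% confidence interval, so it will be reported as a result.

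The time outcome is listed. Its name promises a reduction, yet the planned analysis has no comparator, difference or interval from which a reduction could be read.

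**Working it through.** **Diagnostic Yield.** The plan states no expected value for this measure, so there is no figure to reproduce. The planning count in section 9.2 does reproduce: 150 patients × 1.5 to 2 lesions = 225 to 300.

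Let TP and FP be the true and false mHRME HSIL calls. Let *a* be the share of TP, and *b* the share of FP, that the clinician read as non-HSIL. I take the clinician call as the HRA read, because section 9.1 names as comparator the Lugol's-"guided physician diagnosis of HSIL during HRA".

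- Yield as written: (a·TP + b·FP) / (TP + FP)
- Histology-confirmed yield, same denominator: a·TP / (TP + FP)
- False-positive share of the counted yield: b·FP / (a·TP + b·FP)

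Inputs from the documents: 300 lesions and 30% HSIL (section 9.2); mHRME sensitivity/specificity 94/92 (opening summary) or 93/87 (section 2.1).

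Assumed, because the documents give no figure: clinician HRA sensitivity/specificity 80/30 or 90/50. With reads independent given histology, *a* = 1 − clinician sensitivity and *b* = clinician specificity. In a second scenario, 90% of mHRME false positives are also called HSIL at HRA, so *b* = 0.10. That scenario still treats misses at HSIL lesions as independent.

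At 94/92: TP = 300 × 0.30 × 0.94 = 84.6 and FP = 300 × 0.70 × 0.08 = 16.8, total 101.4. At 93/87: TP = 83.7 and FP = 27.3, total 111.0.

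| mHRME | Clinician (assumed) | Reads | As written | Confirmed | FP share |
|---|---|---|---|---|---|
| 94/92 | 80/30 | independent | (16.92 + 5.04)/101.4 = 21.7% | 16.7% | 23.0% |
| 94/92 | 90/50 | independent | (8.46 + 8.40)/101.4 = 16.6% | 8.3% | 49.8% |
| 94/92 | 80/30 | 90% shared | (16.92 + 1.68)/101.4 = 18.3% | 16.7% | 9.0% |
| 94/92 | 90/50 | 90% shared | (8.46 + 1.68)/101.4 = 10.0% | 8.3% | 16.6% |
| 93/87 | 80/30 | independent | (16.74 + 8.19)/111.0 = 22.5% | 15.1% | 32.9% |
| 93/87 | 90/50 | independent | (8.37 + 13.65)/111.0 = 19.8% | 7.5% | 62.0% |
| 93/87 | 80/30 | 90% shared | (16.74 + 2.73)/111.0 = 17.5% | 15.1% | 14.0% |
| 93/87 | 90/50 | 90% shared | (8.37 + 2.73)/111.0 = 10.0% | 7.5% | 24.6% |

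At an assumed 50% HSIL the shares are 11–30% (94/92) and 17–41% (93/87) with independent reads, and 4–8% and 7–12% with 90% shared.

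*Direction.* The yield as written is a weighted mean of *a* and *b*, so added false positives raise it only if *b* > *a*. A perfectly specific device would give 20% (clinician sensitivity 80%) or 10% (90%). At 94/92 these become 21.7% and 16.6% with independent reads, but 18.3% and 10.0% with 90% shared. The yield can rise, fall or stay put.

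**Time.** In the order of Appendix 1, step 19, let H be HRA, P proflavine application and probe insertion, M the stamped mHRME interval, and B the biopsy block. If the total includes biopsy, which section 9.6 does not say, T = H + P + M + B. The two summarised quantities are T and M. T − M = H + P + B, and T exceeds it by M, which cannot be negative. The only within-patient contrast they offer is thus approximately the added mHRME time.

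It is approximate because P falls between the HRA-end and HRME-start stamps. With assumed minutes H = 10, P = 2, M = 8, B = 6: T = 26, stamped mHRME time is 8, and the time added over H + B = 16 is 10.

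**The case against.** The best defence is that Objective 1 already compares the methods against histology: the model there "will compare SN and SP of each method on a per biopsy and per patient basis". Lost specificity would be visible there, and mHRME-only calls, confirmed and unconfirmed, are the discordant cells of those paired tables. That stands, and it confines the problem to the efficiency measure. It does not change what Diagnostic Yield itself reports.

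It is also fair that Biopsies Averted carries a qualifier implying a truth standard, that no test or decision rule rests on the yield, and that the primary outcome is untouched. On time, the plan summarises total time as well as mHRME time, and the manual's stamps allow components to be recovered.

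A reader might infer three stronger things that the documents do not support:

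- *That a less specific mHRME must score a higher yield.* This needs *b* > *a*, and the shared-error scenario above shows no rise.
- *That a particular share of the yield is false.* The opening summary calls visual HRA identification poorly specific but gives no number, and nothing is said about dependence between reads.
- *That the extra Lugol's-positive normal sites inflate the yield further.* The definition speaks of lesions the clinician classified, and the manual records HRA reads at abnormal areas only. Section 5.1 gives 225–300 images right after describing the extra site, so adding 150 such sites to 300 lesions does not fit it.

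**Conclusion.** Both parts hold on the text. The Diagnostic Yield numerator has no truth condition, so any mHRME false positive that the clinician read correctly at HRA counts as gain. No assumption about accuracy is needed for that, only the reading of *clinician* as the HRA read. The size is unknown: the illustrations span 4% to 62% of the counted yield, they rest on assumed clinician accuracy, assumed dependence and in part an assumed prevalence, and none is a property of the plan. The reduction in procedure time named as an outcome is not estimated by anything in section 9.6.

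These are secondary measures, so the point is a recommended change and not a threat to the primary result. It is worth making because the histology needed is already being collected.

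**What to change.** 1. **Diagnostic Yield.** Keep the denominator of mHRME-diagnosed HSIL lesions. Require consensus-histology HSIL in the numerator at a stated threshold (AIN 2+, with AIN3+ also reported), and take the pre-mHRME HRA read as the clinician call. Report mHRME-only calls not confirmed by histology beside it. Restrict the measure to HRA-visualised lesions with a recorded HRA read, and report Lugol's-positive sites separately.
2. **Biopsies Averted.** Tie *appropriately* to the same histology, and report histologic HSIL wrongly down-graded beside it.
3. **Time.** Rename the outcome *total procedure time and added mHRME time*. State whether the total includes biopsy. Count added time from the HRA-end stamp to the HRME-end stamp, so that proflavine application and probe insertion are included. Claim no reduction from these data. Label any modelled saving from averted biopsies exploratory, because biopsy time is stamped only for the whole block.

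The cost is mainly wording in sections 1.2, 9.5.2 and 9.6. Section 5.1 puts a biopsy at each image site, and the manual records the reads and stamps. The manual shown is for one clinic, so the second site's forms should be checked for the same fields. The downside for the sponsor is that, on the same lesions, the reported yield can only stay the same or become smaller, and the trial no longer claims a time reduction.

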 - a. Record scope in time, HRA start time (page 12)
 - b. Record first abnormal area as Biopsy 1 (page 13)
 - i. Describe lesion, mark location, take anoscopy image
 - ii. Record clinician HRA read, plan (standard of care)
 - c. Go onto second abnormal area as Biopsy 2 (page 14)
 - i. Describe lesion, mark location, take anoscopy image
 - ii. Record clinician HRA read, plan (standard of care)
 - d. Repeat above steps for each abnormal area using extra biopsy pages if necessary
 - e. Record HRA end time. Apply Proflavine, insert HRME. Record HRME start time.
 - f. Proceed to first abnormal area (Biopsy 1)
 - i. Once feed is in focus, freeze HRME
 - ii. Record clinician read and plan based on HRME image
 - iii. Analyze image. Record image number and score.
 - iv. Ask clinician if they are happy with this image or if they would like to take another. Take as many images as needed, using extra biopsy pages if necessary
 - v. Select best image of site (most representative)
 - g. Go onto Biopsy 2.
 - i. Once feed is in focus, freeze HRME
 - ii. Record clinician read and plan based on HRME image
 - iii. Analyze image. Record image number and score.
 - iv. Ask clinician if they are happy with this image or if they would like to take another. Take as many images as needed, using extra biopsy pages if necessary
 - v. Select best image of site (most representative)
 - h. Repeat above steps for each Biopsy using extra biopsy pages if necessary
 - i. Record end HRME time. Remove HRME attachment and insert biopsy forceps. Record biopsy start time.
 - j. Proceed to Biopsy 1, biopsy area. Place sample in labeled specimen container. Record specimen label.
 - k. Repeat for each biopsy.

- 1. Record biopsy end time.
- m. Record scope out time.

Within 2 Days of the Clinic:

20. Within 2 days of the procedure, CRC calls the study participant and complete the Follow Up Symptoms form. Be sure to provide the study participant with CRC and PI phone number (business card/consent form) in case of any adverse events. Any adverse events or serious adverse events reported during the phone call should be reported to PI within 24 hours of being reported. If applicable, the CRC and PI will complete the Serious Adverse Event form. The PI will inform the local and IRB of record if needed within 5 days.

Within 30 Days of the Clinic:

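### Biopsies averted counts only correct down-grades, so it does not vary with mHRME sensitivity, and no efficiency measure debits a down-graded HSIL or an added unnecessary biopsy

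*Combined protocol and SAP*

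**What the plan says.** Section 9.5.2 names the outcome: "The first secondary outcome is efficiency (number of potential biopsies averted, reduction in procedure time".

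Section 9.6, Objective 2a, gives clinical efficiency three components:

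- **Biopsies averted:** the percent of HRA-visualized lesions "originally categorized as potentially needing a biopsy but on mHRME were appropriately down-graded, averting an unnecessary biopsy".
- **Diagnostic Yield:** "Percent of HRME diagnosed HSIL lesions that were classified as non-HSIL by clinician".
- **Procedure time:** total and mHRME time, summarized descriptively.

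The planned inference is limited to intervals: "For Diagnostic Yield and Biopsies Averted, we will estimate 95% confidence intervals". The section states no target, margin or test for these measures, and it does not combine them.

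The Manual of Operations (Appendix 1, step 19) collects what a fuller comparison needs. At each abnormal area the coordinator is told first to "Record clinician HRA read, plan (standard of care") and later to "Record clinician read and plan based on HRME image". Section 5.1 has every imaged site biopsied, so histology should exist for each down-grade.

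**The concern.** A change of biopsy plan can save an unnecessary biopsy, skip a biopsy over HSIL, add a biopsy that finds HSIL, or add one that does not. Biopsies averted counts only the first. The word appropriately keeps a down-graded HSIL out of the numerator, but a reader of the result cannot tell whether few or many HSIL lesions were down-graded to obtain the saving.

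Diagnostic Yield does not supply the debit. It counts mHRME-positive lesions that the clinician had called non-HSIL, does not require histology to agree, and treats a higher value as better. A false up-grade, which would mean an extra unnecessary biopsy, therefore raises it.

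The stake is the secondary claim that mHRME makes HRA more efficient. Section 2.2 rests the rationale on more selective biopsies, and the saving is a figure likely to be quoted alone. As defined, it cannot separate a sensitive device from an insensitive one.

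**Working it through.** **Inputs**

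- Prevalence: "HSIL prevalence of 30" per cent (section 9.2). Applying it per lesion is an assumption; 20% to 50% is shown below.
- Lesions: "median number of lesions per patient is approximately 1.5-2" (section 9.2), in 150 evaluable patients.
- Accuracy: sensitivity (SN) 94% and specificity (SP) 92% from the pilot trial in the opening summary; 93% and 87% from section 2.1. Other SN and SP values below are hypothetical.
- Assumptions: all visualized lesions are planned for biopsy on HRA, the mHRME plan follows the mHRME read, and appropriately means non-HSIL on histology.

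**The plan's own figure.** 150 x 1.5 = 225 and 150 x 2 = 300, which reproduces the 225-300 lesions in section 9.2. The plan gives no expected value for biopsies averted.

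**Formulas, as a share of planned lesions**

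- Biopsies averted = (1 - prevalence) x SP
- HSIL down-graded = prevalence x (1 - SN)
- HSIL share of down-grades = HSIL down-graded / (HSIL down-graded + averted)

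SN does not appear in the first line.

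**Results at 30% prevalence**

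| Device | Averted | HSIL down-graded | HSIL share of down-grades |
|---|---|---|---|
| SN 94%, SP 92% | 0.70 x 0.92 = 64.4% | 0.30 x 0.06 = 1.8% | 1.8/66.2 = 2.7% |
| SN 80%, SP 92% | 64.4% | 0.30 x 0.20 = 6.0% | 6.0/70.4 = 8.5% |
| SN 70%, SP 92% | 64.4% | 0.30 x 0.30 = 9.0% | 9.0/73.4 = 12.3% |
| SN 93%, SP 87% | 0.70 x 0.87 = 60.9% | 0.30 x 0.07 = 2.1% | 2.1/63.0 = 3.3% |
| SN 50%, SP 95% | 0.70 x 0.95 = 66.5% | 0.30 x 0.50 = 15.0% | 15.0/81.5 = 18.4% |
| All negative | 70.0% | 30.0% | 30.0% |
| Perfect | 70.0% | 0% | 0% |

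The hypothetical device that misses half of all HSIL scores above both sets of preliminary figures.

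**Other prevalences.** For SN 93%/SP 87%, SN 94%/SP 92% and all-negative in turn, averted is 69.6%, 73.6% and 80.0% at 20% prevalence; 52.2%, 55.2% and 60.0% at 40%; and 43.5%, 46.0% and 50.0% at 50%. The order does not change.

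**Illustrative counts.** With 300 planned lesions (90 HSIL, 210 not) and SP 92%, 210 x 0.92 = 193.2 are averted, while down-graded HSIL rises from 5.4 (SN 94%) to 18 (80%) and 27 (70%). Section 5.1 puts total images at 225-300 and also requires at least one Lugol's-positive site per patient. If that total includes one such site in each of 150 patients, only 75 to 150 abnormal lesions remain, and these counts are at least halved. The percentages stand.

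**Diagnostic Yield.** Write it as a/b, where b is all mHRME-positive lesions. Adding k false up-grades gives (a + k)/(b + k), which is larger whenever a < b.

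**The case against.** The main reply is that missed HSIL is already the primary outcome. Sections 9.5.1 and 9.6 report SN and NPV with intervals, per lesion and per patient, and an all-negative device would show a primary SN of 0%. If every abnormal area is planned for biopsy, the plan follows the read, and normal sites hold no HSIL, then down-graded HSIL as a percent of planned HSIL is exactly 1 - SN. This stands as far as it goes. But SN and NPV rest on the mHRME diagnosis at all imaged sites, including the Lugol's-positive ones, not on the change of plan among HRA-planned lesions. The plan does not set them against the saving.

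Diagnostic Yield does see up-grades, so added calls are not invisible. They are scored as a gain and on the read alone, which is not a debit.

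It can also be said that Objective 2a only estimates correct down-grades and claims no net benefit. That is fair, and it limits the harm to interpretation. Taking down-graded lesions alone as the denominator would make the measure behave like an NPV, but the definition takes its percentage of HRA-visualized lesions.

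A reader might infer that the whole efficiency comparison rewards a device that always reads negative. The documents do not support that. The effect is confined to one component; even there it is a tie, because any device with SP 100% reaches the same maximum; and an all-negative device has no Diagnostic Yield (0/0).

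A reader might also want to count added biopsies from the Lugol's-positive sites. Those are sites the study itself requires, and step 19 describes recording an HRA plan for abnormal areas only, so they give no sound basis for a net figure.

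**Conclusion.** The point holds for the Biopsies averted component of a secondary outcome. It is insensitive to SN by construction: 64.4% at 30% prevalence and SP 92%, whether 1.8% or 9.0% of planned lesions are down-graded HSIL, with a 70% ceiling shared by a perfect and an all-negative device. No other efficiency measure debits a down-graded HSIL or an added unnecessary biopsy.

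The percentages rest on 30% prevalence per lesion and on all visualized lesions being planned for biopsy. If only some are planned, the level changes but SN still does not enter. Under the all-planned assumption no biopsy can be added at an abnormal area, and the documents give no figure from which to size that part.

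A reader might infer that the trial could pass an insensitive device. It would not: primary SN and NPV would show poor sensitivity, and the primary conclusion is unaffected. The defect lies in what the efficiency figure can support when read alone.

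**What to change.** In section 9.6, Objective 2a, add a cross-table of HRA plan (biopsy or not) by mHRME plan (biopsy or not) by consensus histology at the AIN 2+ threshold, for the abnormal areas where step 19 records both plans. Beside Biopsies averted, report with 95% confidence intervals that allow for clustering by patient:

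- (a) planned biopsies down-graded by mHRME that were HSIL, as a percent of all down-graded lesions and of all HSIL planned for biopsy;
- (b) biopsies added by mHRME, split by histology, and the net change in biopsies.

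Report the Lugol's-positive sites separately and leave them out of the net figure. No weight between a missed HSIL and a saved biopsy is needed, since the components are shown side by side.

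The cost is SAP wording and one extra table. For abnormal areas both plans and the histology are already collected, so no new data are needed. The downside is a less favourable efficiency figure.
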